**Figure 5: Online calculator to estimate sample size (29).**

This sample size is realistic as Prehab receives on an average of 127 annual patient referrals per year.

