## 1. Introduction

### 1.1. Background

Lung cancer is the most common cause of cancer-related deaths in Wales (1). Although surgical resection for early-stage lung cancer with curative intent remains the primary treatment, patients with significant smoking related underlying cardiopulmonary disease and impaired pulmonary function, dyspnoea, frailty and decreased activity levels are unfit for surgery and referred for alternative treatment (2,3). Secondly, individuals who proceed to lung resection, thoracic surgery and general anaesthesia may have direct effects on their respiratory system potentially leading to postoperative pulmonary complications (PPCs), which increases hospital morbidity, prolongs hospital length of stay (HLOS) impacts on the quality of life (QOL) of patients and adds to health-care costs (4). Our aim is to evaluate whether incorporating a breathing training device, POWERBreathe into the existing standardised thoracic prehabilitation program (Prehab) will optimise unfit patients physically for surgery, and following surgery reduce their risk of developing PPC's, reduce HLOS and improve QOL of patients and improve service outcomes (5).

The PRIMROSE study aims to compare two groups of patients referred for Prehab who have lung cancer treatable with surgery: (A) standard Prehab and training with the inspiratory muscle training (IMT) device; and (B) standard Prehab alone, in non-small cell lung cancer patients (NSCLC) undergoing lung resection surgery, with clear primary and secondary outcome measures.

One hundred and thirty-four patients will be recruited for the study (67 for each arm) and with an anticipated attrition rate of 25%, one hundred patients will finally be studied (6,7). With 134 recruited and an attrition rate of 25%, only 100 will remain (50 in each arm). The primary outcome measure tested will be the proportion of patients in each group experiencing postoperative pulmonary complications (PPC), which will be graded I-V using the Clavien Dindo Classification (8). PPCs will be broadly classified as minor (grade 1) and major complications (grade 2-5 where 5 is death). What we want to learn from this RCT study is whether IMT helps reduce grade  $\geq 2$  PPCs to either grade 1 or no complications and thereby help shorten the length of stay in hospital for patients undergoing lung resection surgery.

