## 2. Objectives and Design

### 2.1. Trial Objectives

**Primary Objective:** A randomised controlled trial to evaluate the impact of thoracic PRehabilitation with Inspiratory Muscle tRaining cOmpared to Standard prEhabilitation in surgical lung cancer patients [PRIMROSE Trial].

**Recruitment rate:** The study aims to recruit 134 patients for randomisation over twelve months, with 67 randomised to the intervention group and 67 to the control group (6).

**Retention rate:** These are high-risk patients and a high attrition rate in this population is considered normal. We anticipate the retention of 50 patients in each arm following 1:1 randomisation, and is based on our previous study (15), which showed that following assessment, 6.8% NSCLC patients fail to attend Prehab and 1.1% died prior to commencing Prehab. Likewise, following Prehab, 75.8% patients are ready to proceed with surgery. The attrition rate is an estimate and is anticipated attrition to be 20%-25%.

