### 3. Subject Selection

#### 3.1. Number of subjects and subject Selection

Daily screening of new prehab referrals by the principal investigator or research team, using a consecutive sample approach will be used for participant recruitment. This means selecting all patients who meet the eligibility criteria. Patients over a 12-month period (from January 2025) will be approached to gain consent. However, if recruitment numbers are an issue the study will be extended by six months.

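### An average of 127 referrals a year does not support randomising 134 patients in twelve months, and the extension, study duration and end-of-study number do not fit that target either

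*Protocol*

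**What the plan says.** - **Target and period.** Section 2.1: "The study aims to recruit 134 patients for randomisation over twelve months", 67 per arm. Section 3.1 gives the same window: "Patients over a 12-month period (from January 2025) will be approached to gain consent".
- **Source of patients.** Section 3.1: "Daily screening of new prehab referrals by the principal investigator or research team, using a consecutive sample approach will be used for participant recruitment". Section 2.2 makes the trial single-centre. No other source is named.
- **Feasibility statement.** Section 2.4.1, under Figure 5: "This sample size is realistic as Prehab receives on an average of 127 annual patient referrals per year".
- **Contingency.** Section 3.1: "However, if recruitment numbers are an issue the study will be extended by six months".
- **Attrition.** Section 1.1 uses 25% to go from 134 recruited to 100 studied. The Synopsis and Section 2.1 give 20% to 25%.
- **Duration and end of study.** The Synopsis gives a study duration of two years. Section 4.9 defines the end of the study by 100 patients recruited and twelve months of follow-up.

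**The concern.** The feasibility sentence offers 127 as evidence that the planned size can be reached, yet the number to be randomised in one year is larger than 127. The 127 is also a count of referrals, not of participants. Section 3.3 removes patients with several clinical contraindications, those who decline, and those who do not attend or die before Prehab starts. Others will decline the trial itself.

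At stake is whether the trial reaches the 50 analysed patients per arm on which its stated 80% power rests. If recruitment runs slower than planned, the protocol gives inconsistent signals about what happens next: the extension does not fit the stated duration, and the end-of-study definition is met at a number well below the randomisation target. A sponsor or ethics committee relying on the feasibility sentence would not see this.

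**Working it through.** **Inputs from the protocol:** 134 to randomise (Section 2.1); 12 months, with a possible further 6 (Section 3.1); 127 referrals a year on average (Section 2.4.1); attrition 20% to 25% (Section 2.1); 100 patients analysed (Section 1.1); losses before Prehab of 6.8% and 1.1% in the earlier study (Section 2.1).

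**Input not in the protocol:** the share of referrals that will be eligible and consent. It is assumed below, over a range.

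**1. Reproduce the target.** 100 / (1 − 0.25) = 133.3, rounded up to 134; per arm 50 / 0.75 = 66.7, rounded up to 67. Both match. At 20% attrition the target would be 100 / 0.80 = 125.

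**2. Twelve months.** Share of referrals needed = 134 / 127 = 105.5%. If all 127 were randomised, the shortfall is 7. The number left is 127 × 0.75 = 95, or 127 × 0.80 = 102. Time to 134 at 100% uptake = 134 / 127 × 12 = 12.7 months.

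**3. Removing only the pre-Prehab losses.** 127 × (1 − 0.068 − 0.011) = 117 a year, so 134 / 117 × 12 = 13.7 months. This is kept apart from the attrition figures: Section 2.1 cites these losses as part of the basis for retention, while Section 3.3 lists them as exclusions. Applying both could count them twice.

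**4. With the extension.** Referrals in 18 months = 127 × 1.5 = 190.5. Share needed = 134 / 190.5 = 70.3%.

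**5. Range of assumed conversion** (share of all referrals randomised; 25% attrition):

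| Assumed conversion | 12 months: randomised / left | 18 months: randomised / left | Months to reach 134 |
|---|---|---|---|
| 80% | 102 / 76 | 152 / 114 | 15.8 |
| 70% | 89 / 67 | 133 / 100 | 18.1 |
| 60% | 76 / 57 | 114 / 86 | 21.1 |
| 50% | 64 / 48 | 95 / 71 | 25.3 |

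**6. Year-to-year variation.** 127 is an average. If the yearly count is assumed to be Poisson with mean 127, a year with 134 or more referrals has a probability of about 28%, but every patient would then have to be randomised. At 90% uptake (mean 114.3), the probability of 134 in twelve months is about 4%.

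**7. Duration.** 12 + 12 = 24 months already fills the two years. With the extension, 18 + 12 = 30 months, which is 6 over.

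**8. End of study.** 100 recruited × 0.75 = 75 left (80 at 20% attrition), against 100 required.

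**The case against.** **The sample size called realistic may mean the 100 analysed.** The sentence follows the calculation of 50 per arm, so this is a natural reading, and 100 is below 127. But attrition occurs after randomisation, so more than 100 must be enrolled. Even at the favourable 20%, 125 of 127 referrals (98.4%) would be needed in twelve months. The objection softens the wording of the sentence but does not make it adequate support.

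**The plan has a contingency.** This stands in part. A reader might infer from 134 against 127 that the target cannot be reached at all. The documents do not support that: the impossibility applies to the twelve-month window at the average referral rate. With the extension, 80% conversion reaches 134 in about 16 months. What is missing is any evidence for a conversion of 70% or more.

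**Nothing says the trial closes short.** This also stands. A reader might infer that the trial will shut at month 12 or 18 with far fewer than 50 per arm. No section closes it at either date, and at 70% conversion 18 months leaves about 100 patients, which is 50 per arm. A large shortfall at month 18 depends on an assumed conversion below 70%.

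**Referrals may grow.** Section 1.2 expects referrals from all South Wales health boards by 2027. Recruitment from January 2025 ends by mid-2026 even when extended, so that growth cannot be relied on.

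**This is a timeline matter.** Slow recruitment biases no estimate and leaves the primary analysis unchanged. That is accepted, and it limits the severity.

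**Conclusion.** The point holds in this form: the feasibility statement in Section 2.4.1 is not supported by its own figure. Randomising 134 in twelve months needs 105.5% of average annual referrals. With the extension it needs about 70%, a rate for which the protocol offers no basis. At assumed conversions of 80%, 70%, 60% and 50%, reaching 134 takes about 16, 18, 21 and 25 months.

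Two related inconsistencies need no assumption about conversion. Using the extension gives 30 months against a stated two years, and the end-of-study definition refers to 100 recruited where the target is 134. The latter may be loose wording for the 100 finally studied, but as written it is met by a number that leaves about 75 after 25% attrition.

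The conclusion rests on 127 being a fair average for the recruitment period and on Prehab referrals being the only source. It does not establish that the trial will be underpowered; that depends on a conversion rate nobody has stated. Severity: should be fixed.

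**What to change.** 1. **Section 2.4.1.** Replace the feasibility sentence with the calculation: referrals per month (127 / 12 = 10.6) × proportion eligible × proportion consenting, using the service's own screening data. Check the result against 134 randomised, not 100 analysed.
2. **Sections 2.1 and 3.1, and the Synopsis.** Set the recruitment period from that calculation, and state a study duration that covers recruitment, any extension and twelve months of follow-up. If the calendar cannot be lengthened, state instead the number the trial will deliver in the time available. The length should come from the service's data; the conversion rates used here are assumptions and should not be written in as a base case.
3. **Section 4.9.** Make the end-of-study definition refer to the number that must be randomised.
4. **Sections 2.1 and 3.3.** Say whether non-attenders and deaths before Prehab count as attrition after randomisation or as exclusions before it.

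These are wording changes to the protocol and need no additional patients beyond the 134 or extra procedures. The cost is a longer and less favourable stated timeline, with whatever funding and approvals follow from it.

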## Data collection

QoL data using EORTC QLQ-30 questionnaire will be collected at initial assessment (T0) and on completion of Prehab (T1) as final assessment, then post-surgery at discharge (T2) and at 1 month following surgery (T3).

Subjective outcome measures data include dyspnoea score, PS, thoracoscore, frailty index (FI), LOA and objective measures include 6-minute walk distance test (6MWD) at initial assessment (T0), after every two weeks in Prehab to assess for improvement, and finally at final assessment prior to participants proceeding to surgery (T1) (14,15,30). LOA, measured using the Borg scale of perceived exertion, will be recorded as sedentary, moderately active or active and supplemented by the 6MWD. The 6MWD will be performed using a 10m corridor instead of 30m (31). A 10 metre track along a flat corridor, will be used to measure the distance walked in metres within the 6 minutes. A 10m track was used in our previously published study and proved very effective. The American Thoracic Society guidelines state a distance of 30 metres (100 foot) should be used, however this is difficult practically. It is rare to find a 30-metre corridor in a hospital that is quiet and can allow a chair to be positioned for seated rests. A 10 metre track will be better from a health and safety point of view, as well as giving patient's privacy to focus on the self-paced walk test. These above outcome measures are already standard care for all Prehab patients (14,15).

Calculating the thoracoscore for each individual for lung resection in percentage describes the mortality risk of the individual for surgery. This is already standard operating procedure (SOP) for obtaining informed consent for lung resection surgery, and will be calculated for each participant (T0 and T1) (2,32).

The maximal inspiratory pressure (MIP) for both groups will be measured using a POWERbreathe device (Figure 2) at initial assessment (T0), on completion of Prehab (T1) and at discharge (T2). Measuring MIP is not standard practice for Prehab and will be an additional and essential outcome measure. It is required to assess the progress of each individuals improvement with the Prehab. Due consideration regarding IMT contraindications in patients to avoid harm or adverse events is included in our inclusion/exclusion criteria.

Following surgery, data on PPC's and HLOS will be collected by the researcher. This is standard practice for the prehab service.

**Post-discharge assessment:** Our primary objective is to determine whether IMT prior to surgery with Prehab helps reduce PPC following surgery, which is up to the point of discharge from hospital (alive or dead). This is one time point. Hence, it is anticipated that all patients will complete the discharge assessment for complications. Thus, the study is not underpowered for the primary end point.

Mortality rates will be collected at discharge, 1 month, 3 months, and 365 days post-surgery.

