#### 3.2. Inclusion Criteria:

Lung cancer patients with surgically resectable disease who are referred for pre-treatment optimization with Prehab from the lung cancer Multi-Disciplinary Teams (MDTs). The referral criteria for Prehab is one or more of the following (15):

- $\geq 1$  Medical Research Council (MRC) dyspnoea score
- $\geq 1$  World Health Organization (WHO) performance status (PS)
- Age  $\geq 70$  years
- Frailty index  $>3$
- Borderline or poor pulmonary function (forced expiratory volume in one second (FEV1)  $< 50\%$  or diffusion capacity for carbon monoxide (DLCO)  $< 50\%$ )
- Sedentary patients despite having adequate FEV1 or DLCO

Additionally:

- Surgical resection can be performed, including endobronchial excision of tumour, or lobectomy, segmental resection, pneumonectomy or wedge resection, either via a minimally invasive approach or a standard thoracotomy approach
- Patients will be included in the trial if they are capable of providing verbal written consent for Prehab, and written consent for undergoing surgical resection for lung cancer
- Are over 18 years of age
- All patients will be considered regardless of their baseline respiratory muscle strength

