**Cardiovascular exercises:** namely, stationary cycle ergometry and upper and lower limb resistance exercises will be performed, whilst monitoring the heart rate, blood pressure and oxygen saturations (15). The rate of perceived exertion (RPE) will be measured using the Borg breathlessness scale and used twice at every session to measure the intensity at which each patient is working and guide them to increase or decrease their effort as required.

**Home Exercise Program (HEP):** individualised home exercise programme includes daily walking plan and stair climbing exercise (15). Training enabling them to maintain activities of daily living following surgery. The HEP will be continued following discharge after surgery.

**Health education and smoking cessation advice** will be provided to all current smokers prior to surgery and support following surgery (15). Where necessary nicotine replacement therapy will be provided.

**Intervention group:** The intervention group will receive IMT in addition to a standard Prehab protocol (as above). An MIP in cmH2O, obtained at or greater than 1.5 seconds will be recorded, and the highest MIP of 3 valid breaths will be used as baseline. The IMT pressure in cmH2O will be set initially at 40% of the patients MIP. Participants will be taught to use the device in an upright position and instructed to perform six sets of six breaths with the resting times between each set of breaths reducing from 60 seconds, to 45 seconds, to 30 seconds, to 15 seconds, to 5 seconds. IMT will be used twice-daily preoperatively in the intervention group and not post operatively. Training load intensity on the IMT will be

increased preoperatively by the patient according to the rate of perceived inspiratory effort, on a modified Borg scale.

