#### 4.6. Follow up Procedures (if applicable)

Outcome measures (as highlighted in the above diagram) will be assessed using the European Organisation for Research and Treatment of Cancer (EORTC) quality of life (QoL) questionnaire, the EORTC QLQ-30 (9).

- commencement of Prehab (T0).
- every two weeks of Prehab
- On Prehab completion (prior to surgery) (T1).
- following surgery at the time of discharge from hospital (T2).
- one-month post-surgery (T3).
- 3 months post-surgery (T4).
- 12-month post-surgery (T5).

Outcome measures will be assessed via the telephone or face to face in the cardiothoracic physiotherapy department at Morriston Hospital, or the satellite center by the CI or research team.

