## 7.2. Secondary Endpoint Efficacy Analysis

Secondary end points include improvement in dyspnoea score, PS, LOA, Frailty, 6MWD test, MIP and QoL. Differences between groups in categorical variables will be tested with Chi square or Fisher's exact test. For continuous data the student's t test or the Mann-Whitney U test will be used. The Wilcoxon signed rank test will be used to compare MIP and QoL at T0 and T1 and T3.

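### Level of activity is to be measured with the Borg exertion scale, which rates how hard exercise feels and not how active the patient is, so a change in this secondary endpoint cannot be interpreted

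*Protocol*

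**What the plan says.** Section 2.4.1, under Data collection, fixes both the instrument and the recorded form of the endpoint: "LOA, measured using the Borg scale of perceived exertion, will be recorded as sedentary, moderately active or active and supplemented by the 6MWD". That text places LOA at the initial assessment (T0), at two-weekly reviews during Prehab and at the final assessment before surgery (T1). Figure 6 in section 4.5 adds hospital discharge (T2) and one month after surgery (T3).

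LOA is listed as a secondary outcome in section 1.1 and again in section 7.2: "Secondary end points include improvement in dyspnoea score, PS, LOA, Frailty, 6MWD test, MIP and QoL". For categorical endpoints, section 7.2 adds: "Differences between groups in categorical variables will be tested with Chi square", with Fisher's exact test as the alternative.

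The Borg scale appears again in section 4.4, under cardiovascular exercises: "The rate of perceived exertion (RPE) will be measured using the Borg breathlessness scale". The same sentence says that the rating is "used twice at every session to measure the intensity at which each patient is working and guide them to increase or decrease their effort".

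On how follow-up data are obtained, section 4.6 says: "Outcome measures will be assessed via the telephone or face to face in the cardiothoracic physiotherapy department at Morriston Hospital", or at the satellite centre.

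**The concern.** The three LOA levels describe how active a person is. The instrument named to obtain them rates how hard exercise feels while it is being done. These are different quantities, and the protocol gives no bridge from one to the other. Because the protocol names the instrument, this goes beyond a detail that an analysis plan could supply: no analysis can recover activity from exertion ratings.

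At stake is whether an LOA result means anything. A finding that more patients in the inspiratory muscle training arm became active, or that the arms did not differ, would be reported as a statement about activity when the data behind it were ratings of effort.

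**Working it through.** There is no calculation to reproduce. The protocol attaches no effect size, power or sample size to LOA. The check is to set the passages side by side.

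1. **What the instrument measures.** Section 4.4 is the protocol's own account of the Borg rating: it gauges working intensity within a session and guides the patient to do more or less. That is a rating of current effort.

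2. **What the endpoint describes.** The levels run from sedentary to active. Section 3.2 uses the lowest level in the same descriptive sense, as a trait of the patient: "Sedentary patients despite having adequate FEV1 or DLCO". That is not a response to one bout of exercise.

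3. **From rating to level.** Three things are needed and none is stated:
   - the bout or workload to be rated for LOA;
   - the cut-offs that turn a rating into one of three levels;
   - the way in which the six-minute walk distance (6MWD) enters the level.

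4. **Direction.** A high rating can come from a deconditioned patient doing light work or from a fitter patient doing heavier work. Without a fixed workload, one rating is compatible with opposite levels. With a fixed workload, a falling rating would suggest better fitness, which is still not the same as more activity.

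5. **Time points.** The Data collection text describes LOA only up to T1. Figure 6 continues it to T2 and T3. Section 4.6 allows outcome measures in general to be taken by telephone, in which case there may be no exercise to rate.

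6. **Name of the scale.** Section 2.4.1 refers to perceived exertion. Section 4.4 says that perceived exertion is measured with the Borg breathlessness scale. It is not clear that one and the same scale is meant.

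7. **Consequence for the analysis.** The test in section 7.2 compares the arms on the recorded level. Two assessors following the text could put the same patient in different levels. A change over time could reflect the workload chosen, the patient's fitness, the assessor's judgement or activity, and the recorded data would not separate them.

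8. **Size.** None can be given. For a two-level classification with error unrelated to arm, a true difference is multiplied by sensitivity + specificity − 1. The protocol gives neither quantity, the category has three levels, and nothing fixes how the errors would fall.

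**The case against.** **These measures are established in the service.** The Data collection text says that they are already standard care for Prehab patients and cites the service's earlier publications. A workable classification rule may exist there or on the data form. This stands in part: one can say only that the protocol states no rule. But routine use shows feasibility. It does not make an exertion scale a measure of activity, and the protocol names that scale as the instrument.

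**The endpoint can still move.** A reader might infer that LOA cannot register any change. The documents do not support that. What is recorded is a three-level category supplemented by the 6MWD, and an assessor can move a patient between levels. The difficulty is in interpreting such a move.

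**Titration of effort.** A reader might also infer that the rating is held constant because section 4.4 adjusts effort to it, so that the expected between-arm difference is about zero. The documents do not support this either. Section 4.4 describes supervised exercise and gives no target rating. Nothing says that LOA is taken from those sessions, and T2 and T3 fall after Prehab has ended. Only a conditional statement is possible: if LOA were rated in those sessions, the rating would tend to stay level as the patient improved.

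**Telephone assessment.** Section 4.6 speaks of outcome measures in general and does not say that LOA will be taken by telephone. That is fair. The point is only that it may be, and that the stated instrument would then have nothing to rate.

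**Entry criterion.** That being sedentary is also a referral criterion might look like a bias. It is not one: it is one of several alternative criteria, and dyspnoea score, performance status and frailty also serve as both referral criterion and outcome.

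**Small impact.** This stands. LOA is one of seven secondary endpoints named in section 7.2.

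**Conclusion.** The point holds in a limited form. The protocol fixes, for a named secondary endpoint, an instrument that by its own account in section 4.4 measures something else. It states no bout to be rated and no rule from rating to level. Followed as written, neither a change in LOA nor a between-arm difference can be interpreted as a change or difference in activity.

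The documents do not show that the endpoint is incapable of changing, that it is biased towards no difference, or by how much it might be wrong. The primary endpoint (postoperative pulmonary complications) and its sample size are unaffected.

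The conclusion rests on reading the three levels as describing the patient's activity, which is their plain meaning and matches section 3.2. It would weaken if the service holds a written rule that assigns the levels from reported activity. In that case the reference to Borg in section 2.4.1 is itself wrong, and the rule should be put in its place. The correction should be made, but it is not critical to the trial's main question.

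**What to change.** - **Section 2.4.1, Data collection:** replace the Borg scale as the LOA instrument with classification from the patient's reported usual activity. Use one fixed set of questions, cut-offs for the three levels and a stated recall period. Ask them in the same way in both arms, in person or by telephone, at T0, each two-weekly review, T1 and T3. The recall period should be short enough that at T3 it does not reach back into the admission.
- **Figure 6:** drop LOA at T2, or state that it will not be interpreted as habitual activity, because any recall period at discharge covers the hospital stay. Make the time points in section 2.4.1 agree with the figure.
- **6MWD:** do not use it to set the LOA level. It is already an endpoint in its own right in section 7.2.
- **Borg:** keep it as a measure of session exertion only, and use one name for the scale in sections 2.4.1 and 4.4. The conduct of the sessions does not change.

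The cost is a rewritten sentence, a corrected figure and a short question set on the data form, about a minute per visit by estimate. The main downside is possible loss of comparability with the service's earlier series, if that used Borg. Section 3.1 starts recruitment in January 2025 and this protocol version is dated 03/02/25, so some participants may already have an LOA level under the present wording. Their levels should be flagged, and a level from one method should not be compared with a level from the other.
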